
AIM 1: Explore and identify, using qualitative methods, acceptable and appropriate app content and features of the *Sense2Quit App* to support smoking cessation and relapse prevention in PLWH who smoke. We will conduct focus groups, design sessions, and usability assessments with HIV-positive daily smokers, former smokers, and usability experts. This feedback will guide tailoring of the app to this population of smokers.

AIM 2: Conduct a pilot randomized controlled trial to examine the feasibility, acceptability, and preliminary efficacy of the *Sense2Quit App*. We will randomize 60 HIV-positive smokers to the *Sense2Quit App* plus the Fossil Gen5E smartwatch, standard smoking cessation counseling, and nicotine replacement therapy (active condition) versus

standard smoking cessation counseling plus referral to NYC Quitline (control) in order to examine group differences in rate of quit attempts, 7-day point prevalence abstinence, and sustained abstinence.

AIM 3: Employ the RE-AIM framework to assess the potential scale-up of the *Sense2Quit App*.

IMPACT: Given the high rates of tobacco use among PLWH, the Sense2Quit App has considerable potential for reducing morbidity and mortality among PLWH who smoke.

AIM 4: Testing with Confounding Gestures. To improve the accuracy of smartwatch smoking detection within the current version of the app, we will perform additional testing on the smartwatch with participants who will complete a set of hand gestures to distinguish them from smoking gestures.

STUDY TIMELINE

We will implement a 2-year timeline to accomplish study specific aims. The details of the study activities, including development of the *Sense2Quit App* and the detailed timeline for the clinical trial, are listed in **Table 1**.

Table 1.

Timing (Year/Month)	Enrollment Target	Milestones
Year 1	“Just in Time” 1-3	
 Protocol & manual of procedures finalized Institutional Review Board (IRB) approvals Recruitment: Pre-screen potential participants, contact participants from database, advertisements/brochures in local clinics, provider meetings, presentations to community groups about study
		
 Aim 1 – Focus Group Sessions Coding of qualitative data begins
		
 Aim 1 – Design Sessions Code and analyze qualitative data

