Sample Size and Power: The goal of this pilot study is to estimate the cessation rates in each arm to obtain an effect size for future larger studies. To conduct a hypothesis test for the comparison of cessation rates between the two intervention arms will require a minimum 199 people in each arm (total sample=398) for at least 80% power. This calculation was based on a 2-sided test with the type I error of 0.05, and assuming a 20% cessation rate in the *Sense2Quit App* group (intervention) and a 10% cessation rate in the control arm. The 10% difference would be equivalent to a medium effect size (Cohen's $d=0.45$). In this pilot study, we propose a total sample of 60 (30 per group) of whom we expect there to be 20% attrition. Therefore, this study is not powered to detect a significant difference between study arms. Instead, for the sample size (30 per group), this study will have at least 80% probability that the standard error of the cessation rate estimates $\leq 7\%$. We assume that the expected cessation rates range from 10% to 20%, and therefore the sample size is sufficient to provide a power estimation for a larger trial with acceptable reliability.

Recruitment and Retention: Strategies for recruitment and retention are described in the Recruitment and Retention attachment. We will enroll 60 PLWH who smoke tobacco. Inclusion/exclusion criteria are described above.

Screening: Potential study participants will provide verbal informed consent by phone or complete an eConsent form through REDCap prior to completing a phone screening process that assesses eligibility. If eligible, participants will attend a baseline session described below.

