Procedures: Eligible participants will attend a baseline visit at Columbia University School of Nursing. On the day of their baseline appointment, study participants will meet a study staff member who is trained by a nurse. The study staff member will run the baseline appointment. Upon arrival, participants will be asked to blow into a breath analyzer to complete assessment of their study eligibility. Breath samples will be analyzed for exhaled carbon monoxide (CO) levels (in ppm) using a breathalyzer (MicroTM basic Smokerlyzer[®]). After providing written consent, participants will complete a baseline questionnaire (See **Table 3**). They will be asked complete a timeline to follow back to track their cigarette use for the previous 30 days and to complete the Fagerstrom Test for Nicotine Dependence. Survey instruments will be collected through Qualtrics at baseline, and 4 weeks, and 12 weeks after baseline.

Following completion of baseline study instruments, participants will be randomized (1:1) to the App arm or the control arm, stratified by sex assigned at birth. Participants in both arms will undergo a smoking cessation counseling session. Notes from the counseling session will be recorded on RedCap. Participants will receive an informational packet during the counseling session which will consist of: 1) an appointment reminder sheet, nicotine patch information, nicotine gum information, nicotine lozenge information and smoking substitution ideas (Intervention) or 2) a reminder sheet, NYS Quitline information, and smoking substitution ideas (control). Participants in the control arm will be referred to the New York State Smoker's Quitline. Through the Quitline, participants in the control arm can receive NRT if desired and receive additional smoking cessation counseling. A study staff member will follow up to see how many participants called, texted and/or visited the Quitline webpage. Participants in the intervention arm (App arm) will be provided with combination NRT. Participants will be given an 8-week supply of combination NRT and will be instructed to begin using their NRT supply directly after their baseline visit.

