Data Analysis: This is a pilot study to assess preliminary feasibility, acceptability, and efficacy. Descriptive statistics will be used for all analyses. The rate of quit attempts will be calculated as the proportion of smokers who attempt to quit (i.e., no smoking during a 24 hours period); 7-day point prevalence abstinence will be calculated as the proportion of smokers who are biochemically verified (saliva cotinine) 7-day abstinence at a given time point; and sustained abstinence will be calculated as proportion of days of no smoking starting on the quit date among those who attempt to quit. We will provide point estimates and corresponding confidence intervals of these measures for each arm. Because of our small sample sizes, we will obtain Clopper-Pearson exact confidence intervals based on the binomial distribution. Given the small sample size, the purpose of the arms is to monitor for unexpected, gross differences between the two groups. To determine acceptability, we will ask participants in both arms how useful each of the intervention components were (1 = *Not at all useful* to 7 = *Extremely useful*) and whether they would recommend the program to a friend (1 = *Definitely would not recommend* to 7 = *Definitely would recommend*). For the intervention to be deemed acceptable, the mean level for each of these measures would have to be five or

higher. The efficacy of the intervention will be based on saliva- confirmed 7-day point prevalence abstinence at the final study visit. Lost-to-follow-up participants will be included as smokers.

NOT-OD-15-102: Consideration of Sex as a Biological Variable: In accordance with NIH guidance, we will include sex as a biological variable in the study design (enroll equal numbers of males and females), analyses, and reporting. We will report all primary and secondary outcomes separately by sex to enhance rigor and transparency of our findings in addition to including sex in all multivariate models.

AIM 3: Employ the RE-AIM framework to assess the potential scale-up of the *Sense2Quit App*.

In addition to testing the Efficacy of the *Sense2Quit App*, we will concurrently measure the four remaining RE-AIM dimensions⁸⁸ as follows:

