Statistical Design and Data Analysis: This is a pilot study to assess preliminary feasibility, acceptability, and preliminary efficacy. Descriptive statistics will be used for all analyses. The rate of quit attempts will be calculated as the proportion of smokers who attempt to quit (i.e., no smoking during a 24-hour period); 7-day point prevalence abstinence will be calculated as the proportion of smokers who are biochemically verified 7-day abstinence at a given time point; and sustained abstinence will be calculated as proportion of days of no smoking starting on the quit date among those who attempt to quit. We will provide point estimates and corresponding confidence intervals of these measures for each arm. Because of small sample sizes, we will obtain Clopper-Pearson exact confidence intervals based on the binomial distribution. Given the small sample size, the purpose of the arms is simply to monitor for unexpected, gross differences between the two groups. To determine acceptability, we will ask participants in both arms how useful each of the intervention components were (1 = *Not at all useful* to 7 = *Extremely useful*) and whether they would recommend the program to a friend (1 = *Definitely would not recommend* to 7 = *Definitely would recommend*). For the intervention to be deemed acceptable, the mean level for each of these measures would have to be 5 or higher. The efficacy of the intervention will be based on saliva-confirmed 7-day point prevalence abstinence at the follow-up survey. Lost-to-follow-up participants will be included as smokers.

DISSEMINATION PLAN

Tools developed and evaluated during this project have the potential to extend the impact and reach of tobacco cessation for all smokers but specifically for persons living with HIV (PLWH) who smoke. Per the RFA, this study was designed for dissemination (e.g., feasibility/acceptability of the intervention for PLWH) and suitable for the intended context.

Therefore, a multi-faceted dissemination plan targeting various stakeholders is proposed. We will disseminate our findings to technology-oriented and clinical management-oriented audiences. For technology audiences, we will provide enough detail to enable the *Sense2Quit App* to be constructed and used within an appropriate context.

We propose the following dissemination strategies:

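### The pilot is meant to yield an effect size and group differences, but its analysis plan names no between-arm estimate or interval, and its claim of acceptable reliability for planning a larger trial is not supported

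*Combined protocol and SAP*

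**What the plan says.** **Purpose.** Specific Aims, Aim 2, randomises 60 participants "in order to examine group differences in rate of quit attempts, 7-day point prevalence abstinence, and sustained abstinence". Aim 2, Sample Size and Power, says: "The goal of this pilot study is to estimate the cessation rates in each arm to obtain an effect size for future larger studies". The later section Statistical Design and Power repeats that goal almost word for word.

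**Analysis.** Aim 2, Data Analysis, and Statistical Design and Data Analysis both restrict the work to descriptive statistics. The output is defined as: "We will provide point estimates and corresponding confidence intervals of these measures for each arm". On method: "we will obtain Clopper-Pearson exact confidence intervals based on the binomial distribution". On the comparison itself, the later section says that "the purpose of the arms is simply to monitor for unexpected, gross differences between the two groups"; the Aim 2 text says much the same. Neither section names an effect measure or gives an interval for a contrast between arms.

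**Reliability.** Aim 2, Sample Size and Power, states that 30 per group gives at least 80% probability of a standard error of 7% or less for the cessation rates, expected to lie between 10% and 20%. It concludes that "the sample size is sufficient to provide a power estimation for a larger trial with acceptable reliability". The later section draws a similar conclusion about estimation, from the same standard error.

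**The concern.** The quantity that a larger trial needs from this pilot is the contrast between arms. The plan's own planning effect is such a contrast: a 10-point difference, also expressed as d = 0.45. Yet the analysis as written ends with two separate rates and two separate intervals. Someone following it to the letter would not produce the group difference that Aim 2 promises, nor show how uncertain it is.

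The reliability sentence adds to the problem. It tells the reader that the sample suffices for power estimation, but supports this with the precision of one arm's rate. Power for a two-arm trial depends on the difference, which is estimated less precisely than either rate. The full-scale proposal is to be written at the end of Year 2 (Plan for Future Fully Powered RCT), so the way this result is reported matters.

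**Working it through.** **Inputs.** From Aim 2, Sample Size and Power: 30 per arm, rates of 20% and 10%, two-sided 0.05, 80% power, and 199 per arm for a full trial. From Aim 2, Data Analysis: lost participants count as smokers, so denominators stay at 30. The plan gives no confidence level; I assume 95%, in line with its two-sided 0.05.

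**1. Reproduce the plan's figures.** With pooled rate 0.15, the usual two-proportion formula gives

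n = [1.96·√(2·0.15·0.85) + 0.842·√(0.20·0.80 + 0.10·0.90)]² / 0.10² = (0.990 + 0.421)² / 0.01 ≈ 199 per arm.

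This matches. The odds ratio is (0.20/0.80)/(0.10/0.90) = 2.25, and ln(2.25)·√3/π = 0.447, which matches d = 0.45. So the plan's stated effect size is a between-arm measure.

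**2. What the plan would report.** If the results equal the planning rates, Clopper-Pearson gives:
- 6/30: 20%, interval 7.7% to 38.6%
- 3/30: 10%, interval 2.1% to 26.5%

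**3. What is missing.** The risk difference is 0.20 − 0.10 = +10 points. Newcombe's interval combines the Wilson limits of the arms, 9.5% to 37.3% for 6/30 and 3.5% to 25.6% for 3/30:
- lower: 0.10 − √[(0.200 − 0.095)² + (0.256 − 0.100)²] = −8.8 points
- upper: 0.10 + √[(0.373 − 0.200)² + (0.100 − 0.035)²] = +28.5 points

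The half-width is (28.5 + 8.8)/2 = 18.65, about 19 points. The score interval is −8.8 to +28.9, so the choice of method hardly matters. The standard error of the difference is √(0.16/30 + 0.09/30) = 9.1 points.

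**4. The per-arm reliability claim.** The estimated standard error is √[p̂(1 − p̂)/30]. It is 6.8% at 5/30 and 7.3% at 6/30, so over the plausible range the 7% limit is met only with five quitters or fewer. The binomial probability of this is:

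| True rate | True standard error | P(estimated SE ≤ 7%) |
|---|---|---|
| 10% | 5.5% | 93% |
| 15% | 6.5% | 71% |
| 20% | 7.3% | 43% |

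The stated 80% is met at the bottom of the assumed range but not at its middle or top. At 20% the true standard error already exceeds 7%.

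**The case against.** The strongest reply is that this is a pilot which openly says it is not powered to compare arms, that the sample-size goal is worded first as rates in each arm, and that nothing is lost. With denominators fixed at 30, each reported rate gives back its count, and a reader can compute the unstratified difference and its interval. Much of that is true, and it limits the point: the gap is an unnamed measure and an interval left for the reader to work out, not unrecoverable information. It does not remove the point. The same sentence says that the rates serve to obtain an effect size, and Aim 2 separately promises group differences. An interval for a difference needs no hypothesis test, and a small sample is the reason to show it.

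It can also be said that the 7% criterion was only ever about each arm. That is so, but Aim 2, Sample Size and Power, carries it over to power estimation for a larger trial, and the criterion fails on its own terms over part of the assumed range.

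Three stronger readings are tempting, and the documents do not support them:
- **That sex is ignored after randomisation.** Allocation is "stratified by sex assigned at birth", and the paragraph on sex as a biological variable commits to reporting outcomes by sex and to including sex in multivariate models. Only a sex-stratified between-arm estimate is absent.
- **That efficacy would be judged by whether the two intervals overlap.** No such rule appears anywhere in the plan.
- **That the next trial will be sized on the bare observed difference.** The plan says only that a proposal will be written; its 199 per arm rests on assumed rates.

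**Conclusion.** The point holds as a mismatch between stated purpose and planned analysis. No between-arm effect measure or interval is named for any of the three Aim 2 outcomes. References elsewhere to multivariate models, hypothesis testing and intent-to-treat analyses (the sex-as-a-biological-variable paragraph and the Data Safety and Monitoring Plan) do not specify one.

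At the planning rates the unreported result would be +10 points with a 95% interval of about −9 to +29. That is compatible with no effect and with one nearly three times the assumed size. The conclusion about acceptable reliability for power estimation is unsupported, both because it uses the wrong quantity and because the per-arm claim misses its 80% at true rates of 15% and 20%.

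These figures assume 30 per arm in the denominator, observed rates equal to the planning rates with lost participants already counted as smokers, and a 95% level. The finding does not call the trial into question. It is a change that should be made before analysis.

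**What to change.** - **Aim 2, Data Analysis, and Statistical Design and Data Analysis:** add the between-arm risk difference, with a 95% Newcombe or score interval, for 7-day point prevalence abstinence at week 12 and for quit attempts, labelled as estimation only. The two sections describe the time point differently (final study visit against follow-up survey), so name week 12 in both.
- **Sustained abstinence:** this is a proportion of days, so give a between-arm difference with an interval suited to that measure, not a binomial one.
- **Gross-differences sentence:** keep the small-sample caution, but state that the comparison is reported as the estimate and interval above.
- **Both sample-size sections:** replace the reliability sentence with the expected precision of the difference, about ±19 points at the planning rates, and say that planning of the next trial will take the whole interval into account.

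A sex-stratified interval is optional. With about nine quitters expected in total (6 + 3), the strata would be sparse and an unstratified interval meets the need.

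The cost is some wording and one more line of analysis, with no new data, visits or participants. The downside is that the stated reliability becomes less favourable.

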A research study involving a mobile technology intervention for persons living with HIV (PLWH). The research activities will take place in New York City, and data collection will take place at Columbia University. Participants will be recruited online and offline through social networking websites and apps and through local community-based

Figure 2. (a) Visual reminders, (b) Motivational messages will be

organizations, health centers, and local events. The study will test the *Sense2Quit App* for smokers living with HIV.

Participants in the intervention arm will receive Nicotine replacement therapy (NRT). Participants will be provided with an 8- week supply of combination NRT that they will begin after the baseline visit. The quit date will be the date of their baseline visit. Participants will be offered all 3 forms of NRT (patch, lozenge, gum) and will be allowed to choose 2 forms (combination: patch/lozenge or patch/gum) to use.

Participants who smoke 10 or more cigarettes per day will receive the following dosage for their NRT patch: one 21 milligram patch per day for 4 weeks; one 14 milligram patch per day for 2 weeks; and one 7 milligram patch per day for 2 weeks. Participants who smoke less than 10 cigarettes per day will receive the following dosage: one 14 milligram patch per day for 6 weeks and one 7 milligram patch per day for 2 weeks. This is considered the standard clinical treatment, and participants will receive additional instructions on usage of the patch. Participants will be told the risks of using the patch, which include skin irritation, itching, dizziness, headache, rapid heartbeat, and nausea. Participants will also be advised that they can curb additional cravings with their choice of Nicotine gum or lozenge available for purchase over-the-counter.

Setting. The study will be conducted at Columbia University which provides HIV care for a diverse group of more than 2,000 PLWH. A recruitment plan, which outlines how participants will be recruited through the clinic and community-based organizations, is outlined below.

Participants.

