use the app for the duration of the study period. Two days after baseline, a study team member will reach out to the intervention arm study participant to see if they have any questions or issues with the *Sense2Quit App* and/or watch. The study coordinator will be able to access smoking behaviors and subject information through the online dashboard. The study coordinator will also reach out to participants in both arms once a week through phone call to check-in about their quitting process. At 4 and 12 weeks after baseline, participants in both study arms will attend a follow-up visit at the study site. Participants will report a 7-day point prevalence abstinence of smoking cigarettes⁷⁶ and provide a breath sample using Micro^{+TM basic} Smokerlyzer®. They will also be given a follow-up survey with questions asked at baseline and process questions dictated by the primary outcomes that assess usability and acceptability of *Sense2Quit* (see **Table 3**). We will use skip logic features in our study surveys to identify subjects who select certain responses indicating depression, substance abuse, and/or alcohol abuse and referral information will be presented at the end of the survey. Referral information will include contact information for the Comprehensive HIV Program (CHP) at New York- Presbyterian/Columbia University Irving Medical Center, which offers comprehensive care and services for people living with HIV. Participants completing the survey(s) on-site will be asked if they want to be escorted by staff to CHP.

Table 3. Study Measures

Construct	Measures
Demographics	Gender, age, education, income, employment, health insurance, housing, time since diagnosis with HIV, health literacy (measured by S-TOFHLA). ⁷⁵ and co-morbid conditions
Tobacco Use History	Age of initiation, current smoking, daily smoking, e-cigarette use, types of products used, history of quit attempts, prior use of quitline/telephone counseling services
Tobacco Cessation	CO lung/blood concentration, 7-day point prevalence abstinence – Timeline follow-back ^{76, 77} (confirmed with saliva cotinine); number of quit attempts; days of continuous abstinence
Illicit Substance and Alcohol Use	NIDA ASSIST ^{78, 79} , AUDIT-C ⁶⁰
Predictors of Tobacco Cessation	Fagerstrom Test for Cigarette Dependence, ⁸⁰ Readiness to quit ⁸¹
Cravings and Withdrawal	Minnesota Withdrawal Scale ⁸²
Psychosocial Factors	Depression: CESD score ⁸³ ; Anxiety: STAI score ⁸⁴ , Social support ⁸⁵

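### The measure labelled sustained abstinence is a share of smoke-free days that need not be consecutive, so someone who never goes 7 days without smoking can score 85.7%, and the binomial interval planned for it does not fit

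*Combined protocol and SAP*

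**What the plan says.** Aim 2 in the Specific Aims sets out to examine "group differences in rate of quit attempts, 7-day point prevalence abstinence, and sustained abstinence". The rule for the third of these is the same in the Aim 2 Data Analysis and in Statistical Design and Data Analysis: "sustained abstinence will be calculated as proportion of days of no smoking", counted from the quit date and only in people who attempt to quit. A quit attempt needs only 24 hours without smoking. Seven-day abstinence is the "proportion of smokers who are biochemically verified 7-day abstinence at a given time point". The plan promises point estimates and Clopper-Pearson intervals for all these measures in each arm, and counts participants lost to follow-up as smokers.

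Table 3 lists, in its Tobacco Cessation row, a separate item, "days of continuous abstinence". Neither analysis section says what it is for.

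On timing, the Aim 2 Procedures state: "At 4 and 12 weeks after baseline, participants in both study arms will attend a follow-up visit at the study site". On the start of the count, the Overview says "The quit date will be the date of their baseline visit", while the Aim 2 Procedures also allow a date up to a week after baseline.

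**The concern.** The name promises abstinence that lasted. The formula counts smoke-free days wherever they fall, with no limit on lapses and no minimum run. Scattered smoke-free days earn the same score as one unbroken stretch of equal total length.

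This matters because the app is meant to keep a slip from turning into a relapse. The primary outcome looks only at the week before a visit. Of the three cessation outcomes with a stated analysis rule, this is the only other one that could speak to maintenance, and as defined it cannot. An arm could be reported with a respectable level of sustained abstinence although nobody in it stayed abstinent.

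The interval has a related problem. A binomial interval needs a number of people with the outcome out of a number of people. A share of days for each person is not such a count, and the plan does not say what the numerator and denominator would be.

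**Working it through.** The documents give no figure for this outcome, so there is none to reproduce. The check applies the written rule.

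**Inputs.** Score = smoke-free days / days since the quit date (both analysis sections). Follow-up is 12 weeks = 84 days if counting starts at baseline, or 84 − 7 = 77 days if it starts a week later. The week-4 visit is at 28 days.

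**Highest score without a 7-day run.** To avoid 7 consecutive smoke-free days over T days, a person must smoke on at least floor(T/7) days. The maximum score is (T − floor(T/7))/T.

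- T = 84: 12 smoking days, 72/84 = 85.7%
- T = 77: 11 smoking days, 66/77 = 85.7%
- T = 28: 4 smoking days, 24/28 = 85.7%
- T = 83: 11 smoking days, 72/83 = 86.7%

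An exact search over all day patterns gave the same minima. The two statements on the quit date therefore hardly affect the result. The person who smokes every seventh day satisfies the quit-attempt rule, has a longest run of 6 days, and is not 7-day abstinent at either visit. Under any rule requiring an unbroken run from the quit date, that person lapses on day 7.

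**Arm level.** Assume, for illustration, 25 attempters per arm followed for 84 days, or 25 × 84 = 2,100 person-days.

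- Arm A: 10 people never smoke, and 15 have one smoke-free day each. Score: (10 × 84 + 15 × 1)/2,100 = 855/2,100 = 40.7%. Continuously abstinent: 10/25 = 40%.
- Arm B: all 25 have 34 scattered smoke-free days. Score: (25 × 34)/2,100 = 850/2,100 = 40.5%. Continuously abstinent: 0/25 = 0%.

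The written measure barely separates two arms that differ by 40 percentage points in continuous abstinence.

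**Interval.** For Arm A, a 95% Clopper-Pearson interval that treats the 2,100 days as independent trials runs from 38.6% to 42.9%. A t interval on the 25 individual scores (mean 40.7%, SD 49.4 points, standard error 49.4/√25 = 9.9 points) runs from 20.3% to 61.1%. Clopper-Pearson on people, 10/25, gives 21.1% to 61.3%. Pooling days would overstate the precision about tenfold here; the method is sound for a count of people.

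**Coverage of the data.** The only stated recall window for the smoking calendar is 30 days, at baseline. If the same window were used at follow-up, which the plan does not say, the week-4 visit would cover all 28 days. The week-12 visit would cover 30 of the 84 − 28 = 56 days since then, leaving 26 days unrecorded.

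**The case against.** The strongest reply is that little turns on this. Efficacy rests on cotinine-verified 7-day abstinence, the pilot plans no hypothesis test, the formula is stated openly, and the 7-day result will appear for the same arms. That stands, and it limits the weight of the point. It does not remove it: 7-day abstinence at a visit cannot show whether abstinence lasted between visits, so it cannot correct a misleading figure for maintenance.

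A second reply is that counting from the quit date, read with the continuous-abstinence item in Table 3, may mean the unbroken run from that date. The example participant would then score 6/84 = 7.1%. The text does not say this. It fixes where counting begins and takes a proportion of days; it does not require the days to be joined.

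A third reply is that a strict no-lapse rule would score a recovered slip as failure, although recovery from a slip is what the app seeks. This also stands. A reader might infer that only a zero-lapse definition in all randomised participants would do; the documents do not settle that, and the sponsor must choose. Percentage of smoke-free days is a legitimate measure and should be kept under its proper name.

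A reader might also infer that the mislabelled figure will set the effect size for the larger trial. The sample size sections say only that the pilot estimates cessation rates, assumed to be 10% to 20%, and the plan for the future trial does not mention sustained abstinence. That inference is not supported.

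**Conclusion.** The point holds as a mismatch between name, formula and interval for a secondary descriptive outcome. As written, a score of up to 85.7% over 84 days is compatible with never being smoke-free for 7 days in a row. That is a ceiling, not a typical score, and it moves only to 86.7% in the follow-up lengths checked. It rests on the literal reading of the rule and on day-level data being complete. The two-arm illustration rests further on the assumed 25 attempters per arm.

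A reader might infer that the trial's efficacy conclusion is compromised. It is not: the primary 7-day outcome is defined separately and verified biochemically. What is lost is the ability to say anything about maintained abstinence, and an honest interval for the measure that is reported. The change should be made, but the trial does not depend on it.

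**What to change.** Make the same change in the Aim 2 Data Analysis and in Statistical Design and Data Analysis.

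1. Rename the present measure percentage of smoke-free days. Summarise it per participant, and give it an interval based on variation between participants instead of a binomial interval.
2. Report sustained abstinence as a proportion of people, derived from the continuous-abstinence item in Table 3, with the Clopper-Pearson interval and lost participants counted as not abstinent. Give the continuous run in days beside it.
3. Before the data are analysed, state when the count starts in both arms, which requires reconciling the Overview with the Aim 2 Procedures. State also whether a brief slip is allowed, whether the Table 3 item means the current run, the longest run or the run from the quit date, and which denominator is used.
4. Confirm that the item covers the whole period to week 12.

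The cost is wording and one extra tabulation if the item already covers the full period; if not, the follow-up questions need a longer recall window. No extra visits or participants are needed. The downside is a lower reported figure and few events. The assumed cessation rates of 10% to 20% correspond to 3 to 6 people per arm of 30, and sustained abstinence would probably be rarer. With 0 of 30, the exact 95% upper limit would be 11.6%.
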